4.1.4. P value reporting

Although formal hypothesis testing is not planned for the analysis, should any testing be undertaken (e.g., a paired t-test for change in vital signs measurements), p values will be reported per the American Medical Association (AMA) Style Guide. Specifically, in tables, column headers for p values will be referred to as "P value." Actual p values will contain no leading zeros. All p values will be reported as exact numbers to 2 decimal places, regardless of significance, unless they are lower than 0.01, in which case they should be presented to 3 decimal places. Furthermore, in the event a p value is between 0.045 and < 0.050 , three decimal places will be reported. For p values lower than 0.001 will be expressed as " $< .001$."

4.1.5. Duplicate Subject Identification Number

Subjects entered twice with two different subject identification numbers will have the inactive identification number allocated to a dummy site to avoid duplicate information appearing in tables and listings.

5. ANALYSIS POPULATIONS

5.1. Safety Population

The safety population includes all enrolled subjects who received at least one dose of the IP and shall be used for analysis of all safety endpoints (e.g. the incidence of AEs and SPMs).

5.2. Intention-to-Treat Population

The intention-to-treat (ITT) population is defined as all enrolled subjects (subjects receiving an IVRS enrollment date) regardless of whether they received any IP or not. The ITT population shall be used for the analysis of all efficacy endpoints (i.e. ORR, TTR, DoR, PFS, TTP and OS).

5.3. Efficacy Evaluable Population

The efficacy evaluable (EE) population is defined as all ITT subjects who take at least one dose of IP, who have baseline disease measurement and at least one post-baseline disease measurement or PFS event. The EE population should be used for analyses of the following endpoints: ORR, TTR, DoR, TTP, PFS and OS.

For the purpose of the clinical study report (CSR) deliverables, the EE population substitutes the Per-protocol population outlined in the study protocol.

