10. STATISTICAL ANALYSIS OF EFFICACY ENDPOINTS

All efficacy analyses will be performed using the ITT population and the EE population. The ITT population shall form the primary analysis while the EE population shall form the sensitivity analysis of the endpoints.

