10.1.3.2. Progression-Free Survival

Progression Free Survival is calculated as the time from study enrollment, defined as the IVRS enrollment date, until either PD or death (any cause). Subjects without an event (either a documented PD or death) at the time of study end will be censored at the time of their last documented disease assessment or at the IVRS enrollment date if no disease assessment was conducted. A subject with a documented PD directly following a missing assessment, if not having previously had a documented PD, will be censored at the time of the assessment directly preceding the missing assessment.

Missing assessments are defined as 2 or more consecutive missing assessments, considered as > 66 days (during the treatment period) or > 192 days (during the long-term follow-up phase) between the last adequate assessment and the date of the event, or, >94 days if there is no assessment after enrollment and the subject having an event.

Table 1 below includes the event and censoring rules for PFS.

Table 1: Event and Censoring Rules for Progression Free Survival

Scenario	Date Subject has Event or is Censored	Comment
Progression documented at scheduled assessment	EMA and FDA Guidelines: Event date = first disease assessment date where a PD is documented	A subject with a documented PD directly following a missing assessment, if having not

Scenario	Date Subject has Event or is Censored	Comment
		had a PD observed previously, shall be censored at the time of the last documented assessment or the IVRS enrollment date if there is no prior response assessment.
Progression documented between scheduled assessment	EMA Guidelines: Event = date of documented progression. FDA Guidelines: Event data = last scheduled adequate assessment prior to the unscheduled assessment; if no adequate assessment at scheduled visits existed prior to the unscheduled assessment, then event date = date of unscheduled assessment.	
Subject did not progress nor die	EMA and FDA Guidelines: Censored date: date of last adequate assessment without PD; if no adequate assessment existed then censored at date of enrollment.	
Subject died without initial documented progression	EMA and FDA Guidelines: Event date = date of death.	Per FDA Guidelines if the death date is after AMT then the patient is censored at the last assessment date.

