10.1.3.4. Overall Survival

Overall survival is calculated as the time from study enrollment, defined as the IVRS enrollment date, until death due to any cause. Subjects who do not have death data at the time of study end/analysis will be censored at the time they were last known to be alive.

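### The efficacy evaluable population admits unassessed subjects only through a PFS event, so its overall survival analysis selects on the outcome; the effect is small and its direction is not fixed

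*SAP*

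**What the plan says.** Section 5.3 defines EE as ITT subjects with at least one dose of IP "who have baseline disease measurement and at least one post-baseline disease measurement or PFS event". It continues: "The EE population should be used for analyses of the following endpoints: ORR, TTR, DoR, TTP, PFS and OS". Section 10 fixes the roles: "The ITT population shall form the primary analysis while the EE population shall form the sensitivity analysis of the endpoints".

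Section 10.1.3.2 makes progression or death from any cause the PFS event. A subject without an event is "censored at the time of their last documented disease assessment or at the IVRS enrollment date if no disease assessment was conducted". The same section treats assessments as missing when the gap is ">94 days if there is no assessment after enrollment and the subject having an event".

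Section 10.1.3.4 runs OS from enrollment "until death due to any cause" and censors survivors at the date last known alive. Section 3.1 collects survival status every 3 months in follow-up. TTR (10.1.2) leaves out subjects without a response, and DoR (10.1.3.1) covers responders.

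**The concern.** Death is both the OS event and one of the two routes by which an unassessed subject can enter EE. Take two dosed subjects with a baseline measurement and nothing afterwards: one dies on day 40, the other is alive without progression at 18 months. Both have OS data and both count in ITT. EE keeps the death and drops the survivor.

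The entry rule also leaves the term PFS event undefined, while Table 1 in section 10.1.3.2 gives two event rules (EMA and FDA) that differ in what they censor. Two programmers could build different EE sets from the same data.

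At stake is how the sensitivity analysis is read. A gap between ITT and EE OS could come from the selection rule alone. For other endpoints, close agreement could be taken as robustness although the two analyses use nearly the same data.

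**Working it through.** **1. What the entry rule does, by endpoint** (dosed subjects with a baseline but no post-baseline measurement)

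- OS: died or progressed, in EE; alive without progression, out of EE. In ITT the latter contribute follow-up to the date last known alive.
- PFS: those without an event are censored at enrollment in ITT, which is day 1 under section 4.1.2. Subjects censored before the first event do not change a Kaplan-Meier estimate, so removing them changes nothing unless an event falls on day 1.
- TTR and DoR: a responder has a post-baseline assessment by definition. ITT and EE differ by 0 subjects, except a responder with no dose or no baseline measurement.
- ORR: EE does differ, because section 10.1.1 counts unassessed subjects as non-responders in ITT and EE drops some of them.

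**2. Size for OS.** The SAP gives no survival figure and no number of unassessed subjects, so there is no plan figure to reproduce and everything below is assumed. Let u be the unassessed share, 5% or 12%. Assessed subjects have exponential survival with a 12-month median: S(t) = 2^(-t/12), S(6) = 0.7071. Day 94 is 94/30.4167 = 3.09 months.

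*Reading A: only deaths by day 94 count as PFS events.* Half of the unassessed die by day 94; the rest then follow the same exponential, so C(6) = 2^(-(6-3.09)/12) = 0.845.

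ITT(6) = (1-u)·S(6) + u·0.5·C(6); EE(6) = (1-u)·S(6) / (1 - 0.5u)

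| u | ITT, 6 months | EE, 6 months | Difference | Median ITT / EE (months) |
|---|---|---|---|---|
| 5% | 0.6718 + 0.0211 = 69.3% | 0.6718/0.975 = 68.9% | 0.4 points | 11.65 / 11.55 |
| 12% | 0.6223 + 0.0507 = 67.3% | 0.6223/0.94 = 66.2% | 1.1 points | 11.14 / 10.86 |

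*Reading B: any death counts.* Suppose the unassessed have the same prognosis as the rest and everyone is followed for F months. EE then omits only unassessed subjects alive at F:

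EE(6) = [S(6) - u·S(F)] / [1 - u·S(F)]

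| F | S(F) | u = 5% | u = 12% |
|---|---|---|---|
| 6 months | 0.7071 | 69.6% vs 70.7%: 1.1 points | 68.0% vs 70.7%: 2.7 points |
| 60 months | 0.0313 | 0.05 points | 0.1 points |

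If half of the unassessed die by day 94, as in reading A, the 6-month-cut differences are smaller: 0.7 and 1.7 points. The early cut matters because section 3.1 places the first full analysis after up to 2 cycles and the final one 5 years after the last enrollment.

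**3. Direction.** Under reading A, deaths after day 94 are dropped too. Assume a 16-month median for assessed subjects, 8 months for unassessed, and u = 10%. At 12 months:

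- ITT = 0.9·2^(-12/16) + 0.1·2^(-12/8) = 0.5351 + 0.0354 = 57.0%
- Unassessed dead by day 94: 1 - 2^(-3.09/8) = 0.235
- EE = 0.5351/(0.9 + 0.1·0.235) = 57.9%

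EE is now above ITT, so the bias can go either way.

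**The case against.** - **Effect size.** ITT is primary, the trial is single-arm with a safety objective, no formal testing is planned, and all Kaplan-Meier figures are ITT only. With 720 subjects and OS near 69%, the 95% half-width is about 1.96·√(0.69·0.31/720) = 3.4 points, larger than any shift above. This stands and is why the point is minor.
- **Early deaths.** Admitting them avoids the opposite bias of requiring survival to a first assessment. Also true; the fault lies in dropping the unassessed survivors.
- **Day 94.** The rule is open to dispute for deaths. The censoring sentence concerns documented progression, Table 1 counts a death without progression as an event, and its row on extended loss to follow-up keeps the event under EMA rules. On that view late deaths stay in EE and the shift almost vanishes by study close. This limits the size, and it also confirms that the entry rule is undefined.
- **OS in the Safety Population.** It may already be planned, since Table 14.2.6 is listed for all populations. Section 10 names only ITT and EE for efficacy, so this is unclear at best.

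Three stronger readings might be inferred and are not supported. EE is not the only sensitivity analysis for PFS: Tables 14.2.5.1 and 14.2.5.2 give EMA and FDA versions, which test the handling of missed assessments and new therapy. Not every living unassessed subject is excluded: progression recorded in follow-up can be a PFS event and admit the subject. And EE OS is not always too low, as the last calculation shows.

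**Conclusion.** The point holds as a minor one. Under any reading of the entry rule, EE OS drops unassessed subjects who are alive without progression and whose follow-up ITT uses. How many others it drops depends on a definition that the SAP does not give.

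On assumed shares of 5-12% unassessed and a 12-month median, 6-month OS shifts by 0.4-1.1 points if only deaths by day 94 count. If any death counts, it shifts by about 1-3 points at a 6-month cut (equal prognosis) and by at most 0.1 points at 5 years. The sign can reverse when later deaths are excluded and the unassessed do worse. The ITT results do not change.

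For TTR and DoR, and for PFS on this criterion, agreement between EE and ITT is close to automatic and should not be presented as robustness. For PFS that evidence has to come from the EMA and FDA versions.

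**What to change.** Either of two changes is enough:

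1. Remove OS from the EE endpoints in sections 5.3 and 10, and name all treated subjects (the Safety Population, section 5.1) as the OS sensitivity set. State in Table 14.2.6 which populations are meant. If the PFS-event route into EE stays for other endpoints, say which event definition governs it.
2. Define EE without reference to outcome: at least one dose and a baseline measurement.

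The cost is SAP wording and one rerun. Under the second option, unassessed treated subjects stay in the ORR denominator, so EE ORR may be slightly lower and closer to ITT. As an illustration, with an assumed ITT ORR of 30%, 10% unassessed and 70% of those currently dropped, EE ORR is now 0.30/(1 - 0.07) = 32.3% and would return towards 30%. Neither option makes EE more informative for TTR or DoR; the report should say so.

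A PFS rerun that counts IP discontinuation without a post-baseline assessment as an event should not be added. The discontinuation reasons in section 6 include withdrawn consent and transition to commercially available treatment, which would then be counted as progression.

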6. SUBJECT DISPOSITION

A summary of subject disposition (analysis population allocation, subjects entered, subjects discontinued, along with primary reason for both IP and study discontinuation) will be presented for each of the analysis populations (ITT Population and Safety Population) and will be summarized using frequency and corresponding percentage.

Reasons for discontinuing the IP will be collected on the CRF and will be summarised for all subjects with the following categories possible:

- Death
- Adverse event
- Pregnancy
- Progressive disease
- Lack of efficacy
- Recovery
- Withdrew consent
- Non-compliance with the study drug
- Lost to follow-up
- Study terminated by sponsor
- Transition to commercially available treatment
- Protocol violation (specify)
- Other (specified)

Among those who discontinue the IP, the number of subjects who then discontinue from the study versus those that enter follow-up will be summarised.

Reasons for discontinuing the study will be collected on the CRF and will be summarized for all subjects with the following categories possible:

- Screen failure
- Death
- Adverse event
- Pregnancy
- Progressive disease

- Lack of efficacy
- Recovery
- Withdrew consent
- Non-compliance with the study drug
- Lost to follow-up
- Study terminated by sponsor
- Transition to commercially available treatment
- Protocol violation (specify)
- Other (specified)

A summary tabulation will be provided for subjects enrolled by study center. Duration of study participation, defined as the time from IVRS enrollment date to IP discontinuation date (or the date of last visit for subjects still receiving the IP at the time of study close), will be summarized.

A separate listing will be provided for subjects who have signed consent but are not enrolled because of not meeting all inclusion/exclusion criteria (i.e., screen failure subjects). The reasons for screen failure will be tabulated.

Protocol deviations and violations will be presented in a data listing and summarized by categories in summary tables per deviation/violation type using frequency and corresponding percentage of occurrence.

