3. INVESTIGATIONAL PLAN

3.1. Overall Study Design and Plan

This study is a multicenter, single-arm, open label study of POM in combination with LD-DEX in subjects with refractory or relapsed and refractory MM. Approximately 720 subjects who satisfy study inclusion and exclusion criteria will be enrolled into the study (for detailed subject eligibility see sections 7.2 and 7.3 of Protocol CC-4047-MM-010). There are three periods to this study: The screening period (defined as days -28 to 0 prior to start of the investigational product [IP]), the Treatment period starting at the moment of first administration of the IP defined as Cycle 1 Day 1 until start of follow-up, and the Follow-up period which starts at the time of the permanent IP discontinuation and which continues until all subjects have been followed for up to 5 years after the last issued interactive voice/web response system (IVRS/IWRS) enrollment date if still alive and not lost-to-follow-up, or longer if clinically relevant.

Subjects will undergo screening within 28 days prior to Cycle 1 Day 1 and be treated in 28-day cycles. Subjects will remain on treatment with the IP until a specific event, including, but not limited to, progressive disease (PD), intolerance due to toxicity, death, withdrawal of consent, non-compliance with the IP, and becoming lost-to-follow-up.

An outline of study time points and corresponding assessments due at those times are presented in Table 1: Table of Events (see section 5 of Protocol CC-4047-MM-010). Safety assessments will be performed during the Screening period and on Day1 (± 1 day) of each cycle as well as the time of IP discontinuation. Additional safety assessments (hematology, serum chemistry and estimation of renal function) shall be performed on day 15 (± 2 days) of cycles 1 to 6 while vital signs shall also be collected at a follow-up visit to take place within 28 days post discontinuation of the IP.

Pregnancy testing for females of child bearing potential (FCBP) and pregnancy counseling shall be assessed during the Screening period, Day 1 (± 1 day) of each cycle and at the time of the IP discontinuation. An additional pregnancy test for FCBP shall be conducted within 28 days post IP discontinuation.

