Efficacy measurements shall be collected during the Screening period, at Day 1 (± 1 day) of each cycle and within 28 days post IP discontinuation, with the exception of response assessments which will not be collected during the Screening period. Survival status and recording of subsequent anti-myeloma regimens will be recorded within 28 days post IP discontinuation and during the Follow-up period every 3 months (84 ± 14 days).

Note that the visit (or assessment) occurring just prior to initiation of the IP is defined as “baseline” (i.e., Day 1 of Cycle 1). However, data from the Screening period will be substituted for a given measure if data at Day 1 Cycle 1 is not available.

Dose modifications and interruptions of the IP are permitted throughout the study.

Subjects will remain on study until a specific event, including, but not limited to, becoming lost-to-follow-up, death and withdrawal of consent.

The first full analysis of the primary and secondary endpoint will be conducted once all enrolled subjects have completed up to 2 cycles of the IP if having not stopped therapy earlier.

A final, updated, analysis will be conducted at the time of study close, the point when all subjects will have discontinued from the study, i.e. 5 years from the last issued IVRS enrollment date if having not discontinued from the study before this point.

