14.3.2.16.14.1	Treatment Emergent Grade 3 or Higher Neutropenia and Concurrent Infections and Infestations Within Two Weeks: Safety Population
14.3.2.16.14.2	Treatment Emergent Grade 3 or Higher Infections and Infestations and Concurrent Neutropenia Within Two Weeks: Safety Population
14.3.2.16.14.3	Treatment Emergent Grade 3 or Higher Thrombocytopenia and Concurrent Hemorrhage and Bleeding Within Two Weeks: Safety Population
14.3.2.16.14.4	Treatment Emergent Grade 3 or Higher Hemorrhage and Bleeding and Concurrent Thrombocytopenia Within Two Weeks: Safety Population
14.3.2.16.14.5	Treatment Emergent Thrombocytopenia and Concurrent Hemorrhage and Bleeding Within Two Weeks: Safety Population
14.3.2.16.14.6	Treatment Emergent Haemorrhage and Bleeding and Concurrent Thrombocytopenia within Two Weeks: Safety Population
14.3.2.16.15.1	Summary of Second Primary Malignancies (SPM): Safety Population
14.3.2.16.15.2	Summary of Second Primary Malignancies: Time to Onset, Dosing Summary and Incidence Rate per 100 Person-years: Safety Population
14.3.2.16.15.3	Summary of Second Primary Malignancies (SPM): Safety Population Subjects Who Died
14.3.2.16.15.4	Summary of Second Primary Malignancies (SPM): Safety Population Subjects Who are Alive

14.3.2.16.15.5	Summary of Hospitalisations by Primary Cause: Safety Population
14.3.2.16.16	Summary of Non-Treatment Emergent Adverse Events: Intention to Treat Population
14.3.2.17	Treatment Emergent Adverse Events of Special Interest: Deep Vein Thrombosis/Pulmonary Embolism or Polyneuropathy: Safety Population
14.3.2.18	Treatment Emergent Adverse Events of Special Interest Meeting CTCAE Grade 3 or 4 Criteria: Deep Vein Thrombosis/Pulmonary Embolism or Polyneuropathy: Safety Population
14.3.4.1.1	Shift of CTCAE Grades from Baseline to Worst During Study in Laboratory Values (Chemistry): Safety Population
14.3.4.1.2	Shift of CTCAE Grades from Baseline to Worst During Study in Laboratory Values (Hematology): Safety Population
14.3.4.2.1	Shift from Baseline to Worst During Study in ECOG Performance Status: Safety Population
14.3.4.2.2	Shift from Baseline to Best During Study in ECOG Performance Status: Safety Population

Figures Section 14.

Figure Number	Figure Title
14.2.1	Kaplan-Meier Curve for Duration of Response: Intention to Treat Population
14.2.2	Kaplan-Meier Curve for Time to Progression: Intention to Treat Population

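### SAP section 6 ends study participation when IP stops, although section 3.1 keeps subjects on study through follow-up (minor; one descriptive summary affected)

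*SAP*

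**What the plan says.** Section 6 (Subject Disposition) gives the definition: "Duration of study participation, defined as the time from IVRS enrollment date to IP discontinuation date". One exception follows in brackets: "or the date of last visit for subjects still receiving the IP at the time of study close". The same section tabulates reasons for stopping IP and reasons for leaving the study in two separate lists. It also counts, among subjects who stop IP, how many leave the study and how many go on to follow-up.

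Section 3.1 describes the design: "There are three periods to this study", namely screening, treatment and follow-up. The third is described as "the Follow-up period which starts at the time of the permanent IP discontinuation", and it "continues until all subjects have been followed for up to 5 years after the last issued" enrollment date, or longer if clinically relevant. Leaving the study has its own rule: "Subjects will remain on study until a specific event, including, but not limited to, becoming lost-to-follow-up, death and withdrawal of consent". Survival status and later anti-myeloma regimens are recorded every 3 months during follow-up.

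Section 8.1 separately defines treatment duration, from first study drug to the end of the last cycle.

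**The concern.** The definition stops the clock at the date on which section 3.1 opens the follow-up period. A subject whom section 6 counts as having entered follow-up would, by the same section's definition, already have finished participating.

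The number reported as study participation would then mostly describe how long subjects stayed on IP, which section 8.1 already covers. A reader who takes the label at face value would conclude that subjects were observed for much less time than they were.

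**Working it through.** The SAP states no participation figure, so there is nothing to reproduce. The check compares the definitions and then gives an illustration on stated assumptions.

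**1. End points side by side**

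| Item | Start | End | Source |
|---|---|---|---|
| Study participation | IVRS enrollment | IP discontinuation; last visit only if still on IP at study close | Section 6 |
| Follow-up period | Permanent IP discontinuation | Up to 5 years after the last issued enrollment date, or longer | Section 3.1 |
| Leaving the study | – | Events such as loss to follow-up, death, withdrawal of consent | Section 3.1 |
| Treatment duration | First study drug | End of last cycle | Section 8.1 |

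The end of row 1 is the start of row 2, so follow-up contributes nothing to participation. Stopping IP is not among the examples of study exit in row 3. Row 1 differs from row 4 only by the gap between enrollment and first dose, and by using the IP discontinuation date in place of the last cycle end date.

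**2. Two subjects with equal time on study**

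Suppose both are on study for 60 months. One is still on IP at study close and is credited up to the last visit. The other stopped IP earlier and is in follow-up at study close, and is credited only up to the IP stop. Equal time on study gives unequal participation, because the exception in section 6 does not reach subjects in follow-up.

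**3. Illustration of size (all inputs assumed)**

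The SAP gives no expected treatment time or survival. Assume a 3-day gap from enrollment to first dose, IP stopped T months after first dose, and study exit F months after enrollment. One month is 30.4167 days (section 4.1.2).

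Share counted = (T × 30.4167 + 3) / (F × 30.4167)

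| T | Section 6 participation | Share, F = 24 | Share, F = 60 |
|---|---|---|---|
| 3 | 94.25 days (3.1 months) | 94.25/730.0 = 12.9% | 94.25/1825.0 = 5.2% |
| 6 | 185.5 days (6.1 months) | 185.5/730.0 = 25.4% | 185.5/1825.0 = 10.2% |
| 12 | 368.0 days (12.1 months) | 368.0/730.0 = 50.4% | 368.0/1825.0 = 20.2% |

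These are shares for single hypothetical subjects, not predictions of the summary. For a subject who dies, withdraws or is lost when IP stops, the share is 100% and the definition does no harm.

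**The case against.** The strongest reply is that nothing of consequence depends on this variable. OS runs from enrollment to death, with censoring when last known alive (section 10.1.3.4). PFS, TTP and DoR have their own event and censoring rules (sections 10.1.3.1 to 10.1.3.3). Treatment-emergent adverse events use a window of 28 days after the last dose (section 11.1.1). The 6-, 12- and 24-month rates are Kaplan-Meier estimates. Correcting the definition changes none of them. The start and end dates are stated openly, and no legible table title in Appendix B names the variable. All of this stands, and it is why the point is minor.

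A reader might infer that follow-up would go unreported. The documents do not support that. Appendix B lists Table 14.1.2.2 on disposition in long-term follow-up, Table 14.2.1.2 on survival follow-up, and Listings 16.2.6.7 and 16.2.6.8. Only titles are given, so whether they report a duration is unknown. They would not in any case correct a figure labelled as participation.

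A reader might also infer that the second primary malignancy rate, planned in a table whose title ends "Incidence Rate per 100 Person-years: Safety Population", would be inflated by dividing follow-up events by on-treatment time. Neither that title nor sections 11.1.1 and 11.1.2 refer to study participation, so the SAP creates no such link. How the denominator of that rate is defined is a separate question.

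Finally, closeness to treatment duration is redundancy and not in itself an error. What remains is that the label and the end date disagree with the study design.

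**Conclusion.** The definition is wrong as written. It contradicts the study periods and exit rule in section 3.1 and the split between IP and study discontinuation in section 6. It also treats subjects on IP at study close differently from those in follow-up.

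The summary would report roughly treatment time as participation and leave out all follow-up for subjects who enter it. No figure for the shortfall follows from the SAP. In the assumed cases with exit at 24 or 60 months, between about 5% and 50% of time on study is counted, but how many subjects resemble those cases is unknown. A large multiple for one long survivor should not be read as the expected effect on the summary.

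The damage is limited to one descriptive disposition summary. Severity: minor.

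**What to change.** In section 6, define duration of study participation as the time from IVRS enrollment to study discontinuation, death or last contact, using data cut-off for subjects still on study. If the interval from enrollment to IP discontinuation is of interest, report it under that name; renaming alone would cure the mislabelling but would leave participation unreported.

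The same wording settles two cases for which the present rule may supply no end date: subjects still on IP at the first full analysis, which precedes study close, and enrolled subjects who never received IP.

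The cost is one sentence and one derived variable, built from disposition and survival follow-up data that the study already collects. No endpoint analysis has to be rerun.
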